#### 10.13. *Study Completion*

All TREATMENT subjects will be followed for 12 months after the index procedure. Data collection will continue up to the point of the Month 12 follow-up visit, including the Holter monitor. The End of Study eCRF will have to be completed at study completion.

#### 10.14. *Source Documents*

It is preferable that original source documents are maintained, when available. In lieu of original source documents, certified copies are required to be maintained. A certified copy is a copy (irrespective of the type of media used) of the original record that has been verified (i.e., by a dated signature or by generation through a validated process) to have the same information, including data that describe the context, content, and structure, as the original. Source documentation includes but is not limited to those items noted in Table 10.14-1.

**Table 10.14-1: Source Documentation Requirements**

Requirement	Disposition
Informed Consent documentation process	Retain at Center
Medical history documents pertaining to eligibility criteria	Retain at Center
Documentation of demographics data	Retain at Center
Physical assessment	Retain at Center
Medication regimen and Changes	Retain at Center
Medical history	Retain at Center
Documentation of isolation confirmation for each Pulmonary Vein	Retain at Center
Printed and signed PDF Console Export Case Data	Retain in subject binder
12-Lead ECGs data including ongoing rhythm	Retain at Center
Signed Technical Source Form	Retain in subject binder
Imaging, per standard of care	Retain at Center
Holter report	Retain in subject binder
Adverse Events	Retain at Center
In the event of a subject death (if requested): 
 
Death narrative
 
Relevant medical records
 
Death Certificate
 
Autopsy report
 
	Submit one copy to BSC, Retain one copy at center

## 11. Statistical Considerations

### 11.1. *Endpoints*

#### 11.1.1. Primary Safety Endpoint

The primary safety endpoint will be evaluated by the safety event free rate at 12 months post-index procedure.

*Primary safety events will consist of a composite of the following device and procedure-related and device-related adverse events.*

*Acute primary safety endpoint events, events occurring up to 7 days post-index procedure or hospital discharge, whichever is later, include:*

- Death
- Myocardial infarction (MI)
- Persistent gastroparesis/injury to vagus nerve
- Transient ischemic attack (TIA)
- Stroke/Cerebrovascular accident (CVA)
- Thromboembolism/ Air embolism\*
- Cardiac tamponade/perforation
- Pneumothorax
- Serious vascular access complications\*\*
- Pulmonary edema/heart failure
- AV block not attributable to medication effect or vasovagal reaction

\* Thromboembolic or air embolic events collected in the study refer to any occlusion of blood vessel(s) that results in clinical symptoms

\*\* Defined as prolongation of hospitalization, requirement of surgical intervention or blood transfusion

*Chronic primary safety endpoint events, events occurring through 12 months post-index procedure, include:*

- Atrial esophageal fistula
- Pulmonary vein stenosis ( $\geq 70\%$  reduction of diameter)
- Symptomatic pericardial effusion
- Persistent Phrenic nerve injury\*\*\*

\*\*\*A non-recovered phrenic nerve injury at 12 months post-index procedure will count as a chronic primary endpoint. The study will collect information on phrenic nerve palsy observed before the end of the index procedure and, in case it occurred, will track information for potential recovery during the study visits.

#### 11.1.1.1. Hypotheses

For all Cohorts:

$H_0$ : The primary safety endpoint event-free rate at 12 months post procedure  $\leq 86\%$

$H_a$ : The primary safety endpoint event-free rate at 12 months post procedure  $> 86\%$

### 11.1.1.2. Sample Size

### 11.1.1.3. Statistical Methods

The 12 month (365-day) primary safety event-free rate will be calculated using Kaplan-Meier methodology. Subjects who withdraw from the study prior to 12 months without experiencing an event will be censored on the date of withdrawal. The 95% one-sided lower confidence limit of the observed safety event-free rate will be compared to the performance goal of 86%. If the lower confidence limit is greater than the performance goal, the null hypothesis will be rejected. The lower confidence limit will be calculated as the pointwise confidence limit using the log-log methodology.

### 11.1.2. Primary Effectiveness Endpoint

The primary effectiveness endpoint will be evaluated by the failure-free rate at 12 months post-index procedure in each cohort.

*Failure defined as:*

- Failure to achieve acute procedural success\* in the index procedure;
- More than one repeat procedure during the blanking period (within 90 days post-index procedure);
- Documented atrial fibrillation, or new onset of atrial flutter or atrial tachycardia event ( $\geq 30$  seconds in duration or from a 10 second 12-lead ECG) between days 91 and days 365 post-index procedure\*\*.
- Any of the following interventions for atrial fibrillation, or new onset of atrial flutter or atrial tachycardia between days 91 and days 365 post-index procedure:
  - Repeat procedure
  - Electrical and/or pharmacological cardioversion for AF/AFL/AT
  - Prescribed a higher dose of any AAD\*\*\* documented at baseline or a new AAD\*\*\* not documented at baseline

\* Acute procedural success is defined as isolation of the all pulmonary veins or anatomical equivalents achieved with the POLARx Cryoablation balloon at the end of the index procedure and as demonstrated at minimum by entrance block using the Cryo Mapping Catheter (Other techniques of assessment are per investigator's discretion)

\*\* Subjects will be monitored for recurrences of the arrhythmias by means of clinical visits, ECG and 24-hour Holter monitoring. Recurrences documented with other devices only (eg. ILR, PM, ICD, CRT) will not be counted as primary effectiveness endpoint events

\*\*\* AADs for endpoint will consist of all Class I/III and any Class II/IV medications taken for control of AF/AT/AFL recurrence

[figure not shown]
#### 11.1.2.1. Hypotheses

$H_0$ : The failure-free rate at 12 months post procedure  $\leq 50\%$

$H_a$ : The failure-free rate at 12 months post procedure  $> 50\%$

#### 11.1.2.2. Sample Size

[REDACTED]

[REDACTED]

#### 11.1.2.3. Statistical Methods

The 12 month (365-day) primary effectiveness failure-free rate will be calculated using Kaplan-Meier methodology. Subjects who withdraw from the study prior to 12 months without experiencing an event will be censored on the date of withdrawal. The 95% one-sided lower confidence limit of the observed effectiveness failure-free rate in each cohort will be compared to the corresponding performance goal. If the lower confidence limit is greater than the performance goal, the null hypothesis will be rejected. The lower confidence limit will be calculated as the pointwise confidence limit using the log-log methodology.

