### 9.2. *Withdrawal*

All subjects enrolled in the clinical study (including those withdrawn from the clinical study) shall be accounted for and documented. If a subject withdraws from the clinical study, the reason(s) shall be reported. Withdrawn subjects will not be replaced.

Reasons for withdrawal include but are not limited to physician discretion, subject choice to withdraw consent, lost to follow-up, or death. While study withdrawal is discouraged, subjects may withdraw from the study at any time, with or without reason, and without prejudice to further treatment. All applicable case report forms up to the point of subject withdrawal and a "End of Study" form must be completed.

Every effort should be made to obtain full information on any ongoing reportable adverse events up to the point of withdrawal. All open reportable adverse events should be closed or documented as chronic. Data collected up to the point of subject withdrawal may be used, unless any local regulations apply. Additional data may no longer be collected after the point at which a subject has been withdrawn from the study or withdraws his/her consent, for whatever reason. If such withdrawal is due to problems related to device safety or performance, the investigator shall ask for the subject's permission to follow his/her status/condition.

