### 9.3. *Lost to Follow-Up*

A subject will be considered lost to follow-up if he/she fails to return to scheduled visits as per Data Collection Schedule (Table 10.1-1), and is unable to be contacted by the study site staff.

The following actions must be taken if a subject fails to return to the clinic for a required study visit:

- The site will attempt to contact the subject to reschedule the missed visit and counsel the subject on the importance of maintaining the assigned visit schedule and ascertain if the subject wishes to and/or should continue in the study.

- Before a subject is deemed lost to follow-up, the investigator or designee will make every effort to regain contact with the subject (3 attempts, including telephone calls and/or a certified letter to the participant's last known mailing address or local equivalent methods, where possible). These contact attempts must be documented in the subject's medical record or study file and in the "End of Study" eCRFs.
- Should the subject continue to be unreachable, he or she will be considered lost to follow-up from the study.

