## 10. Study Methods

### 10.1. *Data Collection*

Each Treatment subject will be followed at index procedure, at pre-discharge visit, at the month 3 follow-up, month 6 follow-up and month 12 follow-up. To reliably capture subject status at study end, the month 12 follow-up must be scheduled within  $365 \pm 30$  days following the index procedure. The data collection schedule is shown in Data Collection Schedule (Table 10.1-1).

Table 10.1-1: Data Collection Schedule

Procedure / Assessment	Enrollment Baseline	Index Procedure (Day 0)	Blanking period			Effectiveness Evaluation period			Repeat (additional) ablation procedure
			Pre-Discharge (0-7 days post procedure)	Day 7 contact  (day 7 + 7 days)	Month 3 Follow-Up (91±14 days)	Month 6 Follow-Up (180±30 days)	Month 12 Follow-Up (365±30 days)	Additional Follow-up	
Informed consent process, including informed consent signature date	X								
Eligibility criteria	X								
Demographics	X								
Medical history	X								
LVEF, LA diameter and LA volume	X 								
Physical assessment	X		X		X	X	X	(X)	
LA assessment imaging and thrombus assessment		(X) 							(X) 
Procedural Data		X							X
3D Mapping information		(X)							(X)
12-Lead ECG	X	X	X		X	X	X	(X)	X
Holter Monitor (24 hours)					(X)	X	X	(X)	
Documentation of intervention for AF/AT/AFL (if any)			X		X	X	X	(X)	
Medications	X	X	X		X	X	X	(X)	X
Protocol Deviations	X	X	X	X	X	X	X	(X)	X
Adverse Event Assessment	X 								

X: Required; (X): Optional, per site standard of care;

 Per investigator's method. It is recommended to have the assessment within 180 days prior to enrollment;

 Assessment of left atrium anatomy, pulmonary veins anatomy and rule-out presence of thrombus is strongly recommended and to be performed according to site's standard of care practice - Assessments can be performed using CT, MRI, pulmonary venogram, ICE, TEE or other;

 It is recommended to have the LA assessment performed within 180 days prior to enrollment;

 If subject is discharged prior to day 7 post-index procedure, a (telephone) contact at day 7 (+ 7 days) is required to assess any post-discharge adverse events and complications;

 Adverse event assessment will be performed as from enrollment until study completion;

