 A 24H Holter monitor is required at 6 and 12 months follow-up for all subjects.

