#### **10.10. Month 12 Follow-up (365 ± 30 days) (in-clinic visit)**

The Month 12 follow-up should be completed between 335 and 395 days post-index procedure.

Data collection during the Month 12 follow-up visit will be recorded on the respective eCRF.

Data collection includes

- Date of visit;
- Physical assessment including at minimum resting heart rate, weight, systolic and diastolic blood pressure;
- Rhythm at time of visit (by means of a 12-lead ECG);
- Holter monitor (24 hours) (required);
- Documentation of intervention of AF, AFL, AT, if any;
- New, discontinued or changes to current Anti-Arrhythmic Drugs and Anticoagulation medication regimen;
- Protocol deviations, if any;
- Reportable Adverse Events, including resolution of ongoing events, if applicable.

In cases of a pre-existing and unresolved phrenic nerve palsy the subject should be assessed to evaluate if the event resolved (method per investigator's discretion).

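### Does the undated loss-to-follow-up rule let Month 12 no-shows inflate the effectiveness rate?

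*Combined protocol and SAP*

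**What the plan says.** Section 11.1.2.3 fixes the estimator and time point: "The 12 month (365-day) primary effectiveness failure-free rate will be calculated using Kaplan-Meier methodology". The one-sided 95% log-log lower limit is compared with the 50% goal of Section 11.1.2.1. The only censoring rule is "Subjects who withdraw from the study prior to 12 months without experiencing an event will be censored on the date of withdrawal".

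Section 9.2 places loss to follow-up inside withdrawal: "Reasons for withdrawal include but are not limited to physician discretion, subject choice to withdraw consent, lost to follow-up, or death". Section 9.3 describes how loss is established. The site tries to reschedule the missed visit, makes three contact attempts, and then: "Should the subject continue to be unreachable, he or she will be considered lost to follow-up from the study". No date is attached to that status.

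On the visit itself, Section 10.10 says "The Month 12 follow-up should be completed between 335 and 395 days post-index procedure", so the window closes 30 days after the day-365 time point. Footnote 6 of Table 10.1-1 says "A 24H Holter monitor is required at 6 and 12 months follow-up for all subjects", and Section 10.13 says "Data collection will continue up to the point of the Month 12 follow-up visit, including the Holter monitor".

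Three other places bear on how the date would be settled. Sections 9.2 and 9.3 call for an End of Study form, Section 12.1 promises CRF completion guidelines, and Section 11.2.7 refers to a Statistical Analysis Plan that can be amended before analysis.

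**The concern.** A subject who attends Month 6 (days 150 to 210) and never returns can be declared lost only after the Month 12 visit is missed and the contact attempts fail. That can easily fall after day 365. If the declaration date is the one recorded, the subject did not withdraw before 12 months and the rule gives no earlier censoring date. Kaplan-Meier then keeps the subject at risk and event-free through day 365.

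The plan wants the Month 12 visit for exactly this purpose ("To reliably capture subject status at study end, the month 12 follow-up must be scheduled within" 365 ± 30 days), and neither Section 11.1.2.3 nor Section 11.3.1 makes its ECG or Holter a condition of failure-free status. Any such credit favours the device, in a single-arm test against a fixed goal with no missing-outcome sensitivity analysis named. At stake are an upward shift in the reported rate and, if the true rate lies near 50%, a higher chance of passing wrongly.

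**Working it through.** **1. What the plan's own figures allow.** The minimum of 199 subjects (Section 7.1) cannot be rebuilt, because the sample-size text is blacked out. The success cut-off can be. With complete data, S = k/199, Greenwood sum v = (199 − k)/(199k), and lower limit = S^exp(1.645·√v/|ln S|).

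- k = 112: S = 56.3%, limit 50.3%, passes.
- k = 111: S = 55.8%, limit 49.8%, does not pass.
- Exact one-sided error: P(X ≥ 112 | 199, 0.5) = 4.4%.
- Power at 199 is 80% for a true 59.0% and 90% for a true 60.5%.

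**2. Assumptions (not in the documents).** Acute failure 5%; first detection 22% by Month 6 and 13% between Months 6 and 12. The true rate is then 0.95 × 0.78 × 0.87 = 64.5%. Loss is 5, 10 or 15%, unrelated to outcome, half of it after Month 6. Between 0 and 60% of recurrences are found between visits. Month 12 visits fall on days 335 to 365.

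**3. Hand check of the shift.** Overstatement = share lost after Month 6 × event-free at Month 6 × failure risk from Month 6 to 12, with 0.95 × 0.78 = 0.741 event-free at Month 6.

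- 5% loss: 0.025 × 0.741 × 0.13 = 0.24 points
- 10% loss: 0.05 × 0.741 × 0.13 = 0.48 points
- 15% loss: 0.075 × 0.741 × 0.13 = 0.72 points

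**4. Simulation under the same assumptions.** Bias is at a true 64.5%; error is at a true 50% with N = 199.

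| Date used for no-shows | Bias, points (5 / 10 / 15% loss) | One-sided error |
|---|---|---|
| Declaration, always after day 365 | +0.2–0.3 / +0.4–0.6 / +0.6–0.9 | 5.1–5.4 / 5.9–6.7 / 6.9–8.4% |
| Half declared early and dated at end of contact | +0.1 to +0.5 overall | 5.0–6.6% |
| End of contact | 0.0 to +0.1 overall | 4.5–4.8% |
| Last rhythm check | −0.2 to −0.9 overall | 2.4–3.9% |

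**5. Could no-shows reverse a result?** The expected number of event-free Month 12 no-shows is 199 × (0.025, 0.05, 0.075) × 0.741, or about 4, 7 and 11. At 128/199 (64.3%), reversal needs 128 − 111 = 17 hidden failures, more than all of them together. At 115/199 (57.8%) it needs 115 − 111 = 4.

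**6. Cost of censoring at the last rhythm check.** At a true 60% with 10% loss, the chance of passing is 0.81–0.82, against 0.85–0.86 with end-of-contact dating and 0.89–0.90 with no-shows credited. The rule reads low partly because it discards event-free time after the last check while keeping recurrences caught in that time.

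**The case for a change.** The strongest case for a change is that a primary test should not rest on a date its own section leaves undefined, when one sentence would settle it. Harsher assumptions also give much larger effects. At 10% loss, with all loss and most failures after Month 6, the overstatement is 1.3 to 1.8 points and the error 10.9 to 15.1%. Suppose instead that 5 to 15% of all subjects are Month 12 no-shows, nothing is detected between visits, and 23 to 33% of those event-free at Month 6 fail by Month 12. The error at a true 50% then runs from 8.3 to 38.8%. In that simple two-visit model, censoring at the last check is unbiased, with an error of 4.5 to 4.6%. No-shows who recur more often than attenders would make the bias larger still.

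Part of this stands: the text is silent on the date, and the direction favours the device. The large figures, however, need loss dated at declaration after day 365, loss and failures concentrated after Month 6, and a true rate at the goal. The documents support none of these. Section 9.3 also narrows the group, since the site first tries to reschedule and only an unreachable subject is lost. Where the visit was booked early, loss can be declared before day 365 and the ordinary rule applies. The advantage of last-check censoring disappears once visits spread over their windows and some recurrences are found between them.

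A tipping-point count would be a reasonable extra. Section 11.2.6 is open-ended enough to allow it, and it is informative only near the goal.

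**Conclusion.** No change to the plan is needed. The point is a missing date definition that analysts fill sensibly. Reading the withdrawal date of a lost subject as the end of contact fits the rule's wording and leaves 0.0 to 0.1 points of bias and a one-sided error of 4.5 to 4.8%. The End of Study form, the CRF guidelines or the SAP can record that convention without altering the method.

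Even under the unfavourable reading, the overstatement is 0.2 to 0.9 points at 5 to 15% loss, and the test is affected only near 50%. At a true 65% the chance of passing is at least 0.98 under all three dating rules. Censoring at the last check would exchange a small possible upward bias for a downward one of similar size and some power near 60%. That is a trade-off and no clear gain.

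These sizes rest on the assumed loss and failure timing in the working and on loss unrelated to outcome. The documents give neither a loss rate nor a failure pattern.

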## 11.2. *Data Analyses*

### 11.2.1. Secondary Effectiveness Endpoint

Documentation and rate of acute procedural success (definition see section 11.1.2.). Electrical isolation of a PV is demonstrated at minimum by entrance block using the Cryo Mapping Catheter (Other techniques of assessment are per investigator's discretion).

Information on isolation method used per site standard of care will be collected with a minimum by entrance block in all PVs or anatomical equivalents. Additional data, if available, will be collected on Exit Block or Conduction Block verification using 3D mapping.

### 11.2.2. Interim Analyses

No formal interim analyses are planned for the purpose of stopping the study early for declaring effectiveness or for futility. Analysis of each endpoint will be performed when all applicable data for that endpoint has been collected. Analyses of acute data (procedural safety and acute procedural success) may be performed and used for publication purposes after completion of study enrollment, index procedure, 7 day and 3 month follow-up of all subjects. A study report will be completed when the first 199 De Novo treatment subjects with paroxysmal atrial fibrillation qualifying for primary endpoint analyses will complete the follow-up of 12 months.

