**POLARx Cardiac Cryoablation system**  
**Post Market Clinical Follow-up study**  
**POLAR ICE**

	
 
• For subjects that will undergo repeat ablation during the course of the clinical follow-up, anatomical location of ablations gaps will be assessed.
 
 
* LA dwell time is defined as time from the Cryoablation Catheter introduced in the left atrium (LA) to the last time of Cryoablation Catheter exiting the LA.
 
Additional ancillary analyses on specific subgroup of subjects, may be presented.
 
These analyses will include but not limited to the following:
 
 
• Age (<60 versus <math>\geq</math> 60 years);
 
• Gender (Male versus Female);
 
• Monitoring (Subjects with data from continuous ECG recording systems (eg. ILR, PM, ICD, CRT) versus those without).
 

Method of Assigning subjects to Treatment	
Any subject who signs the consent form will be considered enrolled in the study.
 
Any subject that signs the consent form, has the study device inserted into the body and undergoes protocol specific treatment for the intended disease (cryoablation) will be assigned to the TREATMENT group.
 
The 12 Month follow-up data from minimum 199 De Novo TREATMENT subjects with paroxysmal atrial fibrillation will serve as PMCF data and an interim report will be generated once the follow-ups are completed.

Follow-up Schedule	
Visits schedule: pre-discharge, 3 months (blanking period), 6 months and 12 months.

Study Duration	
Enrollment is expected to be completed in approximately 12 months; therefore, the total study duration is estimated to be approximately 24 months.

Participant Duration	
The study duration for each subject is expected to be approximately 12 months.

Inclusion Criteria	
 
1. Subjects indicated for the treatment of AF with the cryoablation system according to current and future Guidelines and system indications for use;
 

[figure not shown]
[figure not shown]

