### 7.1. ***Scale and Duration***

Approximately 25 sites in Europe and Middle East will be included in the study.

A minimum of 200 subjects (with the possibility to expand up to a maximum of 400 subjects) will be enrolled in the study. A minimum of 199 subjects with De Novo treatment (i.e. first treatment for AF in the left atrium) for paroxysmal atrial fibrillation (PAF) will be analyzed to establish the continued safety and effectiveness profile of the Cryoablation System and fulfill the PMCF requirements for the submitted labeling of the Cryoablation System. This number represents the minimum number for the primary endpoint statistical hypothesis testing.

The entire study cohort will provide information on real-world usage of the Cryoablation System and will be analyzed for secondary objectives. These will include subgroup analysis in selected subjects of interest (including (but not limited to) De Novo ablation versus repeated ablations). These analyses will be non-powered but in case some of these subgroups will be poorly represented in the study, Boston Scientific may propose in the future to extend the sample size to up to 400 subjects.

Each subject will be followed at specific time points after the index procedure: pre-discharge, at 3 months (blanking period), 6 months and 12 months post-index procedure. Therefore, the study duration for each subject is expected to be approximately 12 months.

Subjects will be monitored for recurrences of the arrhythmias by means of clinical visits, ECG and 24-hour Holter monitoring.

Study enrollment is expected to be completed in approximately 12 months. Therefore, the total study duration is estimated to be approximately 24 months.

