## 9. Subject Accountability

### 9.1. *Point of Enrollment*

Investigators will select subjects who are appropriate for study inclusion as per eligibility criteria as specified under section 8.2 and 8.3. Subjects who have given written informed consent are considered enrolled in the study. All enrolled subjects will be counted against the enrollment ceiling of maximum 400 subjects. A total of 199 De Novo TREATMENT subjects with paroxysmal atrial fibrillation will serve for PMCF reporting purposes. No study-related activities, testing, procedures, etc. can take place until the Informed Consent Form (ICF) is signed and dated by the subject. Screening tests that are part of standard of care can be used to determine pre-eligibility. Data from exams performed prior to consent/enrollment (e.g. TTE) will be collected as medical history data after the subject is consented/enrolled in the study. It is the investigator's site responsibility to assess eligibility criteria before obtaining the Informed Consent Form.

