## 11.3. *General Statistical Methods*

### 11.3.1. Analysis Sets

Effectiveness endpoint analyses will use all available data from all eligible TREATMENT subjects. Eligible TREATMENT subjects for the primary effectiveness endpoint includes all TREATMENT subjects who do not have an implantable continuous ECG recording system (eg. Pacemakers, arrhythmia loop recording systems, ICD, CRT). Eligible TREATMENT subjects for the secondary effectiveness endpoint will include all TREATMENT subjects.

Primary safety endpoint analyses will use data from all available TREATMENT subjects. Safety analysis for ATTEMPT subjects will be limited to the Acute primary safety endpoint events (per definition in section 6.2.1.).

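### The plan does not fix one confirmatory analysis set and one analysis time for the two primary tests

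*Combined protocol and SAP*

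**What the plan says.** **De Novo paroxysmal AF subjects, at least 199.** The synopsis and sections 7.1 and 7.2 give 199 as the minimum number for the primary hypothesis tests. Section 9.1 words it as a fixed total: "A total of 199 De Novo TREATMENT subjects with paroxysmal atrial fibrillation will serve for PMCF reporting purposes". Section 11.2.2 makes it the earliest such subjects: "A study report will be completed when the first 199 De Novo treatment subjects with paroxysmal atrial fibrillation qualifying for primary endpoint analyses" complete 12 months. For the same data, the synopsis (method of assigning subjects to treatment) says "an interim report will be generated once the follow-ups are completed".

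**TREATMENT subjects at large.** Section 11.3.1 says "Effectiveness endpoint analyses will use all available data from all eligible TREATMENT subjects". It then defines eligibility for the primary effectiveness endpoint only by the absence of an implanted continuous ECG recorder. For primary safety it uses all available TREATMENT subjects. Neither set is limited to De Novo or paroxysmal AF, or to a number.

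**Undefined cohorts.** Section 11.1.1.1 states the safety hypotheses for all cohorts. Section 11.1.2.3 says "The 95% one-sided lower confidence limit of the observed effectiveness failure-free rate in each cohort will be compared to the corresponding performance goal". No section defines a cohort.

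**Level and timing.** Each test is one-sided at 5%; for safety, "The 95% one-sided lower confidence limit of the observed safety event-free rate will be compared to the performance goal of 86" percent. Section 11.2.2 adds: "Analysis of each endpoint will be performed when all applicable data for that endpoint has been collected". On growth, section 7.1 says "Boston Scientific may propose in the future to extend the sample size to up to 400 subjects".

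**The concern.** In a single-arm study the conclusion rests on one confidence limit against one fixed goal, so the set of subjects and the date of analysis are part of the test. Here two statisticians could each follow the text and compute different limits: one in De Novo paroxysmal AF subjects, the other in a mixed set that includes repeat ablations and non-paroxysmal AF.

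Two things are at stake. First, the mixed set may have a different true rate, so a pass or fail there does not answer the question posed for De Novo paroxysmal AF. Second, if results from more than one set or time are available and either can be presented as the primary result, the stated 5% error rate no longer holds.

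**Working it through.** **The plan's own figure.** The 199 cannot be reproduced. The sample-size text is blank or redacted in the public copy, so expected rates, power and attrition are not available. The check below needs none of them.

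**Step 1: which sets the text allows.**

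| Source | Primary set | Time |
|---|---|---|
| 11.2.2 | first 199 qualifying De Novo paroxysmal AF | when those 199 reach 12 months |
| Synopsis, 7.1, 7.2 | De Novo paroxysmal AF, 199 or more | called an interim report in the synopsis |
| 11.3.1 | all TREATMENT (effectiveness: without implanted recorder) | not stated |
| 11.1.1.1, 11.1.2.3 | undefined cohorts | 12 months post procedure |

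The sets differ even without expansion, because enrolment is open to AF generally and to repeat ablations. Collecting 199 De Novo paroxysmal AF subjects will probably leave a larger TREATMENT set.

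**Step 2: pass mark for one test at 199.** Inputs: goals of 50% and 86%, one-sided 95% log-log limit (sections 11.1.1.3 and 11.1.2.3). Assumption: no censoring, so the Kaplan-Meier estimate is s = x/n.

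Lower limit = s^exp(1.645 × se), with se = √[(1 − s)/(s·n)] / |ln s|.

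- Effectiveness, 112/199: s = 0.5628, se = 0.06248/0.5748 = 0.1087, limit = 0.503, a pass. With 111/199 the limit is 0.498, a fail.
- Safety, 180/199: s = 0.9045, se = 0.02303/0.10035 = 0.2295, limit = 0.864, a pass. With 179/199 it is 0.858, a fail.

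Exact binomial chance of passing when the true rate equals the goal: P(X ≥ 112 | 199, 0.50) = 4.4% and P(X ≥ 180 | 199, 0.86) = 3.9%.

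**Step 3: two tests, either one counting.** This scenario is not stated in the plan. Let r₁ and r_N be the pass marks at 199 and at final N, and p₀ the goal. Take X₁ ~ Bin(199, p₀) and, independently, X₂ ~ Bin(N − 199, p₀).

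P(either) = P(X₁ ≥ r₁) + Σ over k < r₁ of P(X₁ = k) × P(X₂ ≥ r_N − k)

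| Final N | Effectiveness r_N | P(either) | Safety r_N | P(either) |
|---|---|---|---|---|
| one look at 199 | 112 | 4.4% | 180 | 3.9% |
| 210 | 118 | 5.1% | 190 | 4.3% |
| 220 | 123 | 5.7% | 198 | 5.6% |
| 250 | 139 | 6.1% | 225 | 5.3% |
| 300 | 165 | 6.8% | 269 | 5.7% |
| 400 | 217 | 7.6% | 356 | 6.9% |

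The safety column does not rise smoothly because the pass mark moves in whole subjects. A normal approximation with correlation √(199/400) = 0.705 gives 8.0% at 400, which is consistent.

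**Step 4: how far N can go.** The ceiling of 400 counts every consented subject, including Consent Ineligible, Intent and Attempt (section 9.4). The effectiveness set also drops implanted recorders. The stated reason to expand is to fill under-represented subgroups, with De Novo versus repeated ablation as the named example. The rows near 210 to 220 are therefore more relevant to De Novo paroxysmal AF than the row at 400.

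**The case against.** A reader might infer that the plan tests both hypotheses at 199 and again on up to 400 subjects, so that the false-positive rate exceeds 5%. The documents do not support that.

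- No section orders a second primary test.
- The synopsis and section 7.1 assign the entire cohort to secondary objectives, with subgroup analyses described as non-powered. Expansion is optional and serves those subgroups.
- Section 11.2.2 plans no formal interim analysis for early stopping. Its sentence on timing reads most naturally as one analysis per endpoint. An interim report can simply be the primary report issued before the study closes.
- No section says that either of two results would count as success.
- If the later set is all TREATMENT subjects, the true rate may differ, and the common-rate calculation in step 3 does not then give the error rate for one null.
- With the sample-size text redacted, the absence of an alpha allocation can be stated only for the visible text.

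All of this stands, and it makes the inflation conditional. It does not remove the contradiction. Section 11.3.1, the section that defines the analysis sets, does not carry the De Novo paroxysmal AF restriction. The interim disclaimer covers early stopping only, not a success claim at 199 followed by another in a larger set. And if the set can be chosen after both results are known, reporting just one test does not restore the 5%.

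**Conclusion.** The point holds as a contradiction over the confirmatory set and time, not as demonstrated alpha inflation. Followed literally, the sections give pass/fail results in different populations and at different times, each at an unadjusted one-sided 5%.

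The possible cost in error rate depends on three assumptions: two nested tests, the same true rate in both sets, and either result counting as success. The calculation also ignores censoring. Under these the false-positive rate per endpoint goes from 4.4% to about 5.7% (effectiveness) and from 3.9% to about 5.6% (safety) at a final N of 220. The 7.6% and 6.9% at 400 are upper bounds. If one test is designated in advance, there is no inflation from this source.

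**What to change.** - In sections 11.1.1.3, 11.1.2.3 and 11.3.1, restrict the primary hypothesis tests to De Novo paroxysmal AF TREATMENT subjects; for effectiveness, also to those without an implanted continuous recorder.
- State that each hypothesis is tested once, in one named set at one named time. Choose either the first 199 qualifying subjects by index-procedure date, or all qualifying subjects at the end of follow-up. Both control the error rate. Because effectiveness has the extra exclusion, say whether the 199 are counted separately for each endpoint.
- Label every other analysis, including all TREATMENT subjects and any expanded cohort, as descriptive: estimate and interval, no pass/fail.
- Delete or define the cohort wording in sections 11.1.1.1, 11.1.2 and 11.1.2.3, and use one description of the 199 throughout, including section 9.1 and the synopsis.

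The cost is wording only, with no extra subjects. Under the first-199 option, qualifying subjects beyond 199 contribute only descriptively. If the sponsor already intends a single test, the edit simply records it.
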